FFPE	Formalin fixed paraffin embedded blocks
FGFR1	Fibroblast Growth Factor Receptor 1
fMRI	Functional MRI
FOSTER	Fighting OsteoSarcoma Through European Research
GCP	Good clinical practice
GDPR	EU General Data Protection Regulation 2016 (EU)2016/679
GeCIP	Genomics England Clinical Interpretation Partnership
GRC	Global rating of change Scale
Hb	Haemoglobin

HRA	Health Research Authority
HRD	Homologous Recombination Deficiency
ICH GCP	International Conference of Harmonisation-Good Clinical Practice
ICONIC	Improving outcome through Collaboration in OsteosarComa
ICGC	International Cancer Genome Consortium
IGF(R)	Insulin-like Growth Factor (receptor)
IO	Immune Oncology
IP	Intellectual Property
ISAP	Independent Scientific Advisory Panel
ISF	Investigator Site File
ISRCTN	International Standard Randomised Controlled Trial Number
IV	Intravenous
LDH	Lactate dehydrogenase
LN	Lymph node
MAMS	Multiarm, multistage study
MAP	High dose methotrexate, doxorubicin, cisplatin
MDM	Medical decision making
MDT	Multi Disciplinary Team
MT1-MMP	Membrane type 1 metalloprotease enzyme contributing to angiogenesis.
mNCA	model Non-Commercial Agreement
MRI	Magnetic Resonance Image
NCITA	
NCRI	National Cancer Imaging Translational Accelerator National Cancer Research Institute
NICE	National institute for health and care excellence
NIHR	National institute for health research
Non CTIMP	Clinical Trial not involving an Investigational Medicinal Product
ORC	Osteosarcoma Research Consortium
OS	Osteosarcoma
PAs	Patient Advocates
PBMCs	Peripheral Blood Mononuclear Cells
PET/CT	Positron Emission Tomography - Computed Tomography scan
PI	Principal Investigator
PIS	Patient information sheet
PPIE	Patient and Public Involvement and Engagement
PRO	Patient Reported Outcome
QoL	Quality of life
R&D	Research & development
rEECur	An international randomised controlled trial of chemotherapy for the treatment of
	recurrent and primary refractory Ewing sarcoma.
REC	Research Ethics Committee
RNOH	Royal National Orthopaedic Hospital
RT	Radiotherapy
RTD	Routes to Diagnosis
SAR	Serious Adverse Reaction
SAM	Sarcoma Assessment Measure
SOC	Standard of Care
TAA	Tumour associated antigens
TESS	Toronto Extremity Salvage Score of function

TMF	Trial Master File
TMG	Trial Management Group
TRACERx	TRAcking non-small cell lung Cancer Evolution through therapy [Rx]
TSC	Trial Steering Committee
TYA	Teenage & young adult cancers
UCL	University College London
UCL CTC	CR UK and UCL Cancer Trials Centre
UCLH	University College London Hospital
WB MRI	Whole body MRI
WGS	Whole genome sequencing
WTSI	Wellcome Trust Sanger Institute

1. PROTOCOL SUMMARY

1.1. Summary of Study Design

Title:	Improving outcomes through Collaboration in OsteosarComa
Short Title/acronym:	ICONIC
Sponsor name & reference:	University College London Reference: 18/0248
Funder name & reference:	Bone Cancer Research Trust
Clinicaltrials.gov no:	NCT04132895
Design:	Prospective observational cohort study.
Overall aim:	To improve treatment and outcomes for patients with osteosarcoma (OS) by establishing a clinically annotated cohort of newly diagnosed patients with OS with longitudinal collection of biospecimens.
Primary objective:	To obtain high quality clinical data and biospecimen collection from OS patients to develop potential new osteosarcoma trials.
Secondary objectives:	To enrol 300-350 patients to address the following questions:
	CLINICAL OBJECTIVES
	 Describe the impact of variation in management of patients with OS across treatment sites in the UK
	 Assess whether tumour margin and response to chemotherapy predict local recurrence in OS
	BIOLOGICAL OBJECTIVES
	Assess whether OS tumour and immune models grown from OS patients can be used to identify new therapeutic targets
	Explore whether new candidate immunotherapy drug targets for OS can be discovered based on cellular and genomic analysis
	 Collect peripheral blood mononuclear cells (PBMCs) from OS patients to inform immune studies
	 Develop patient derived explants, primary cell cultures, cell lines and organoid models from fresh/frozen patient tumour tissue to investigate OS biology and validate new candidate drug targets
	 Use formalin-fixed paraffin-embedded (FFPE) samples to evaluate genetic and immune biomarkers and aid development of novel therapeutic targets and trials
	Create a legacy resource of OS immune oncology (IO) data and patient models to accelerate future collaborative research efforts

	CIRCULATING BIOMARKERS			
	 Assess whether circulating biomarkers can be used as prognostic markers and to predict burden of disease, response to therapy and outcome 			
	Determine the prevalence of Germline DNA alterations in UK OS patients			
	IMAGING OBJECTIVES			
	 Determine if standard of care imaging can be used to conduct imaging biomarker studies through establishment of an imaging repository 			
	Examine the effects of tumour heterogeneity and clonal evolution on chemotherapy response and patient outcome and determine if this can be used to stratify patients for therapy			
	PATIENT EXPERIENCE			
	 Assess the value of the Sarcoma Assessment Measure (SAM) for longitudinal assessment of patient quality of life and identify predictors of variance in patient reported outcomes (PROs) 			
	 Describe the routes and timescales of diagnostic pathways for patients with OS, and assess whether this has any impact on patient outcome 			
Target accrual:	A minimum of 350 patients (including those already recruited in ICONIC).			
Eligibility criteria:	Inclusion criteria			
	 New histological diagnosis of osteosarcoma or in the absence of osteoid seen on biopsy, pathology and imaging supportive of a diagnosis of osteosarcoma 			
	 Written informed consent of patient and/or parent/legal guardian or written confirmation of opinion of person with duty of care where applicable 			
	Exclusion criteria			
	Diagnosis more than four months prior to registration			
Number of sites:	At least 25 sites representing OS specialist oncology and surgical sites across the UK			
Treatment summary:	Treatment will be given as per usual standard of care.			
	No treatments are specified by this protocol.			

Patient study activities:

Clinical data collection

Clinical data will be collected on a regular basis. Data to be collected include baseline characteristics, treatment details, results of key investigations (including blood tests and scans), patient status (including performance status) and outcome.

Tissue and blood collection

- Tissue for FFPE and fresh freezing according to local policy will be collected during routine procedures at diagnosis, at surgery and at relapse if clinically indicated.
 - Optional study specific biopsies will be requested at relapse in cases where a biopsy is not clinically indicated.
- Blood samples will be collected from patients receiving chemotherapy and/or surgery at the same timepoints as tissue, with an additional sample presurgery and further optional samples.

Patient Reported Outcomes (PROs)

Sarcoma Assessment Measure (SAM) questionnaire

Patients ≥13 years of age will be requested to complete a Sarcoma Assessment Measure (SAM) questionnaire along with TESS, EORTC-QLQ-C30 and Global rating of change (GRC) at registration, annually and at relapse.

Prediagnostic data collection

- Patients ≥13 years will be requested to complete a questionnaire at registration detailing symptoms and routes to diagnosis.
- For patients <13 years, the parents/legal guardian will be requested to complete the questionnaire at registration detailing symptoms and routes to diagnosis.

Central laboratory analyses:

Tissue

Frozen tumour tissue will be analysed as part of the 100,000 Genomes project, or through NHS England where possible for WGS, further analyses may be undertaken including RNA and epigenetic analysis as part of Osteosarcoma Research Consortium (ORC).

Fresh/frozen tumour tissue will be used to establish tumour explant, primary cell cultures, cell lines and patient derived organoid models, for validation of new candidate therapeutic targets, including co-culture experiments of organoids/explants together with matched autologous immune cell samples and compound screenings.

	 FFPE tissue will be used to: Determine feasibility of DNA/RNA extraction for validation studies Validate findings from WGS and other analyses including molecular targeted sequencing and copy number analysis Conduct spatial transcriptomics analysis and high dimensional immunohistochemistry analysis 		
	Blood		
	Blood samples will be collected to:		
	Investigate germline alterations		
	 Evaluate two circulating tumour cell (CTC) isolation and characterisation methods: 		
	 Parsortix[™] and DEPArray[™] 		
	Flow cytometry using MT1-MMP Ab		
	 Store for potential methylation profiling, genetic analysis of circulating tumour DNA (ctDNA) and future research 		
	To Inform immune studies blood samples will also undergo Ficoll based centrifugation to obtain fresh PBMCs.		
Duration of recruitment:	To 31 January 2025		
Duration of follow up:	Patients will be followed up for minimum of two years, with a median of approximately 56 months follow up.		
Definition of end of study:	The end of study will be declared two years after recruitment of the last patient.		

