3.1. Study Objectives

3.1.1. Stage 1: Completed

Determined the feasibility of recruiting patients to a national study with high quality clinical data and biospecimen collection to address clinical and biological questions in OS. Its specific research objectives and associated analyses are detailed in Appendix 4 below.

3.1.2. Stage 2

To enrol >350 patients (including those enrolled in Stage 1) and to use the data and samples collected to begin to address the questions listed below.

Following completion of Stage 1 the research objectives of Stage 2 have been amended and adjusted to take into account previous findings:

- Describe variations in management of patients with OS across treatment sites in the UK, including how decisions are reached for tumours being deemed inoperable and how patients contribute to the final decision on surgical operability in terms of what surgery is acceptable.
- Describe current indications for radiotherapy (RT) as part of local therapy
- Describe the impact of variation in management of patients with OS across treatment sites in the UK on patient outcome
- Assess whether tumour margin and response to chemotherapy predict local recurrence in OS
- Use FFPE samples be used to validate WGS findings, identify patients for specific therapies and aid development of novel therapeutic trials
- Use FFPE samples to perform transcriptional and proteomic spatial profiling of OS
- Develop a legacy resource of OS IO data and patient models to accelerate future collaborative research efforts
- Establish novel *in vitro* experimental models of OS (cell lines, organoids, explants) to be used to address biological questions regarding the mechanism of response to chemotherapy and immune-directed therapies
- Create an OS IO data atlas portal
- Assess whether circulating biomarkers can be used as prognostic markers and to predict burden of disease, response to therapy and outcome
- Collect PBMCs from 20 OS patients at UCLH
- · Set up an OS imaging repository with NCITA
- Use two methodologies of circulating tumour cell (CTC) detection to isolate and quantify CTCs in a subset of 50 patients undergoing neoadjuvant chemotherapy
- Describe associations between tumour heterogeneity and clonal evolution on chemotherapy response and patient outcome and determine if this can be used to stratify patients for therapy
- Determine if Germline DNA alterations can be confirmed in OS
- Collect WGS samples for the OS population

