17.1. Sample Size as feasibility endpoint

One of the objectives of Stage 1 was to assess the feasibility of recruiting to this cohort. Our assumption was that 15 sites would be opened during the course of the first 11 months of recruitment. Once all sites were opened (from month 12 onwards), we estimated that the average recruitment rate would be 5 patients/month.

Following the completion of Stage 1 and with the extension to the recruitment period, we expect to recruit a minimum of 300 patients to the study in total.

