7.	Determine feasibility of using standard pathology reporting to assess margin status for risk of local recurrence	 Collection rate of pathology reports in patients undergoing surgery Characterisation of tumour size, assessment of resection margins, % necrosis
Pa	tient Reported Outcome	
1.	Determine feasibility of data collection for validation of a sarcoma assessment measure (SAM) in patients undergoing treatment for OS	 Completion rate of SAM, TESS, EORTC-QLQ-C30 and GRC Descriptive analyses of PROs

17.2.2. Stage 2

17.2.2.1: Support and development of ICONIC infrastructure

The first aims for Stage 2 are:

- to support ongoing recruitment to the ICONIC study with additional follow up to form a cohort of a minimum of 300 patients with a median of approximately 56 months follow up
- to continue the collection of tissues and blood samples for CTC and plasma for circulating DNA (ctDNA)
- to collect peripheral blood mononuclear cells in a cohort of patients for IO research
- to establish an imaging biorepository for collaborative imaging biomarker studies.

Analysis of patient outcomes will be descriptive, using Kaplan-Meier methods for survival outcomes (e.g. overall survival, event-free survival and progression-free survival) and counts/frequencies for categorical outcomes (e.g. pathological response to chemotherapy).

Predictors of patient outcome will be assessed using standard regression techniques: Cox regression for survival outcomes, logistic regression for categorical. We will consider the following potential predictors of patient outcome:

- Blood biomarkers: serum biomics and ctDNA/CTCs
- Baseline characteristics (age, performance status, grade, primary site, tumour size, stage)
- Patterns of treatment
- Tissue biomarkers for IO research

Research questions	Planned analysis
Evaluate serum biomarkers (ALP, LDH) as prognostic markers in OS	Quantify serum biomarkers at baseline (pretreatment) and changes in response to chemotherapy.
	Characterise distribution of serum biomarkers as histograms and ranges (min, max, IQR, median)
	Assess serum biomarkers for prognostic value by using Cox regression (time-to-event outcomes) and logistic regression (categorical outcomes)
Evaluate ctDNA as predictors of response and outcome in OS	Quantify ctDNA biomarkers at baseline (pretreatment) and changes in response to chemotherapy.
	Characterise distribution of ctDNA as histograms and ranges (min, max, IQR, median)

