	Assess ctDNA biomarkers for prognostic value by using Cox regression (time-to-event outcomes) and logistic regression (categorical outcomes)
Evaluate whether two methodologies of circulating tumour cell (CTC) detection can isolate and quantify CTCs in patients undergoing neoadjuvant chemotherapy	Identify and quantify CTC numbers at baseline (pretreatment) and changes to CTC numbers in response to chemotherapy Descriptive analysis of CTC numbers as histograms and ranges (min, max, IQR, median)

Power calculations for analysis of biomarkers as predictors of pathological response:

All power calculations assume a fixed 2-sided 5% significance level. As these analyses are hypothesis generating, no adjustments have been made to account for multiple testing.

Stage 1 determined the good pathological response rate to be lower than in clinical trials with 17/43 (37%) having a good response.

Based on data from England (2011-2015), 66% of patients receive surgery and 66% receive chemotherapy. At the outset of Stage 1 we had assumed that 60% of patients receive both treatments. At the end of Stage 1, we determined in our cohort that 72% of patients were planned to receive both modalities of treatment.

We will therefore assume the size of the full dataset of patients treated with both modalities will be at least 65% of 300 patients, thus 195 patients.

1. Serum biomarkers

We expect at least 90% of patients to provide serum samples for biomarker analysis, giving us a cohort size of 176. Assuming an overall pathological response rate of ~40%, and assuming biomarkers will be

categorised based on the median to give an even split (88 per group), below is a summary of the power we will have to detect varying effect sizes:

Alpha	Proportion responding without biomarker (# of responders)	Proportion responding with biomarker (# of responders)	Odds ratio	Risk ratio	Power
0.05	20% (18)	60% (53)	5.9	2.9	99.9%
0.05	25% (22)	55% (48)	3.6	2.2	98.6%
0.05	30% (26)	50% (44)	2.4	1.7	77.8%
0.05	32.5% (29)	47.5% (42)	1.9	1.4	52.9%

2. ctDNA

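### The protocol gives conflicting totals for the recruitment target (300-350, at least 350, more than 350, at least 300), so whether the target was met cannot be judged

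*Protocol*

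**What the plan says.** Four statements of the total stand in the current text:

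- Section 1.1, secondary objectives: "To enrol 300-350 patients to address the following questions".
- Section 1.1, target accrual: "A minimum of 350 patients (including those already recruited in ICONIC".
- Section 3.1.2 (Stage 2): "To enrol >350 patients (including those enrolled in Stage 1".
- Section 17.1: "we expect to recruit a minimum of 300 patients to the study in total". Section 17.2.2.1 repeats the figure, with the aim to "form a cohort of a minimum of 300 patients with a median of approximately 56 months follow up".

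The power calculations in section 17.2.2.1 name their base. The number of patients treated with both surgery and chemotherapy is taken as "at least 65% of 300 patients, thus 195 patients", and the serum cohort follows from that. The ctDNA cohort is set at 150 out of a total of 300. The immune oncology power in section 17.2.2.2 is given for 150 samples, with no total stated. Recruitment runs to a calendar date, 31 January 2025 (section 1.1).

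**The concern.** The number 350 is the top of the range in one line of the summary, the floor in another line of the same summary, and not quite enough in section 3.1.2. The statistics section uses a floor of 300. A range of 300-350 and a requirement for more than 350 have no value in common.

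Enrolment is written into the objectives, and section 17.1 treats sample size as a feasibility endpoint. Accrual against target is therefore something the study will have to report, and any final number from 300 to 349 would be a success by some sections and a shortfall by others.

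**Working it through.** **Step 1: do the statements describe the same quantity?** Target accrual and section 3.1.2 both say that Stage 1 patients are included. Section 17.1 refers to the study in total. The split into stages therefore does not explain the difference.

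**Step 2: test each statement against possible final totals.**

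| Final total | 1.1 secondary objectives (300-350) | 1.1 target accrual (at least 350) | 3.1.2 (more than 350) | 17.1 and 17.2.2.1 (at least 300) |
|---|---|---|---|---|
| 320 | met | missed | missed | met |
| 350 | met | met | missed | met |
| 351 | outside the range as written | met | met | met |

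No total satisfies all four as worded. The gap between the two floors is 350 - 300 = 50 patients, or 50/300 = 17% of the lower one.

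**Step 3: which total do the power figures use?** Inputs from section 17.2.2.1: total 300; 65% treated with both modalities; 90% of those with serum; 150 patients with ctDNA; a median split into two equal groups; an overall response rate of about 40%. On the test level: "All power calculations assume a fixed 2-sided 5% significance level".

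- Serum: 0.65 × 300 = 195; 0.90 × 195 = 175.5, stated as 176, so 88 per group.
- ctDNA: 150, so 75 per group.

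Power = Φ{[|p1 - p2| - 1.96 × √(2p̄(1 - p̄)/n)] / √[(p1(1 - p1) + p2(1 - p2))/n]}, where n is the number per group and p̄ is the mean of p1 and p2 (pooled variance under the null, no continuity correction).

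For 30% v 50%, p̄ = 0.40:

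- n = 88: [0.20 - 1.96 × √(0.48/88)] / √(0.46/88) = 0.764, so power is 77.8%.
- n = 75: [0.20 - 1.96 × √(0.48/75)] / √(0.46/75) = 0.552, so power is 70.9%.

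All rows, as stated in the protocol and as recomputed:

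| Response rates | Serum, stated | Serum, n = 88 | ctDNA, stated | ctDNA, n = 75 |
|---|---|---|---|---|
| 20% v 60% | 99.9% | 99.99% | 99.9% | 99.96% |
| 25% v 55% | 98.6% | 98.6% | 97.0% | 97.0% |
| 30% v 50% | 77.8% | 77.8% | 70.9% | 70.9% |
| 32.5% v 47.5% | 52.9% | 52.9% | 46.6% | 46.6% |

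Both tables reproduce from 300. The immune oncology statements (over 70% for a risk ratio of 1.7, over 95% for 2.2) also hold at 75 per group, where 30% v 50% gives 70.9% and 25% v 55% gives 97.0%.

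**Step 4: what would 350 give?** This assumes that the same fractions apply.

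- Serum: 0.65 × 350 = 227.5; 0.90 × 227.5 = 204.75, about 102 per group.
- ctDNA: half of 350 = 175, about 87 per group.

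| Response rates | Serum, n = 102 | ctDNA, n = 87 |
|---|---|---|
| 25% v 55% | 99.4% | 98.6% |
| 30% v 50% | about 84% | about 77% |
| 32.5% v 47.5% | 59.1% | 52.4% |

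**The case against.** The best defence is that there are really two positions and not four. A minimum of 300 agrees with the lower end of 300-350, and at least 350 differs from more than 350 by one patient. Section 17.1 states an expected floor, and basing power on the lower end of a range is cautious: if 350 enrol, the stated powers are exceeded. Recruitment ends on a date, no stopping rule or primary test depends on the total, and the biomarker analyses are described as hypothesis generating. The version history records a change to 300-350, which suggests that the other wording is an editing slip.

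Most of this stands, and it limits how serious the point is. It does not remove the contradiction. The protocol nowhere says that 300 is a conservative base for a target of 350, and even if it did, the range would still conflict with target accrual and section 3.1.2.

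Some stronger readings are tempting but not supported:

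- A reader might infer that the basis of the power figures is unclear, or that the power is wrong. The serum and ctDNA calculations name 300 and reproduce from it.
- A reader might infer that every power figure is tied to 300. The immune oncology calculation gives 150 samples and no total. That equals the ctDNA cohort, but the protocol does not make the link.
- A reader might project accrual at 5 patients a month and conclude that 350 is out of reach. That rate was a Stage 1 assumption for 15 sites, and section 1.1 now plans at least 25. A projection would also need an assumed recruitment start and opening-phase rate.
- A reader might take 350 as a ceiling. Only the range in the secondary objectives reads that way; two other places make 350 a floor or a number to be exceeded.

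**Conclusion.** The point holds as a moderate inconsistency in a stated sample size. The protocol gives conflicting totals for one cohort, with floors 50 patients apart, and a final number such as 320 would both meet and miss the target. It is neither an arithmetic nor a power error. The stated powers are right for 300 and conservative for anything larger.

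The comparison with 350 rests on unchanged fractions: 65% with both treatments, 90% of those with serum, and half of all patients with usable ctDNA samples. On that basis the serum power for 30% v 50% would move from just below 80% to just above it. The conclusion that the targets conflict rests on the wording alone and needs no assumption.

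**What to change.** State one target in sections 1.1, 3.1.2 and 17. The sponsor must choose which, since the documents do not settle it.

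- **If the minimum is 300 (range 300-350):** correct target accrual in section 1.1 and the opening line of section 3.1.2. Section 17 stays as it is. The cost is wording in two places.
- **If the minimum is 350:** correct the secondary objectives in section 1.1 and the figures in sections 17.1 and 17.2.2.1, settle whether section 3.1.2 means at least 350 or more than 350, and add a sentence saying that 300 is a deliberate conservative base for power. The power tables can then stand. Recomputing them for 350 is optional.

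Neither option changes study conduct or data collection.
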